- Cognitive decline will be assessed as a safety assessment during the Core Study (ADAS-cog₁₄, MMSE, and CBB) and during the OLE Phase (MMSE). (revised per Amendment 07) Of particular importance will be the assessment of reaction time testing using the detection and identification tasks on the CBB during the Core Study. (revised per Amendment 07)
- During the Core Study, an assessment of suicidality using the C-SSRS will be performed at Screening, Baseline, and at regular intervals during the Treatment and Follow-up Period (see [Section 9.5.1.5.11](#)). During the OLE Phase, C-SSRS will be performed at Visit 21 (start of OLE treatment) and Visit 32 or the ED Visit (end of OLE treatment). Additional clinical assessments of reported suicidal thinking and behavior will be performed by the investigator at every scheduled visit during the OLE Phase (see [Appendix 6](#)). (revised per Amendment 07)
- All subjects, regardless of whether they complete all 18 months of treatment or prematurely discontinue study drug during the Core Study, will have at least 4 off-treatment Follow-Up Visits during the Core Study (2, 4, 8, and 12 weeks after the last dose of study drug). Subjects who complete or prematurely discontinue study drug during the OLE Phase will have 2 off-treatment Follow-Up Visits at 4 and 12 weeks after the last dose of study drug. (revised per Amendment 07)
- More frequent safety assessments can be made as unscheduled assessments/visits during the off-treatment Follow-Up period, if clinically indicated. (revised per Amendment 04)
- An ophthalmic examination will be conducted at Baseline and if the subject experiences visual disturbances during the course of the Core Study (see [Section 9.5.1.2.1](#)).

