 4. Must have an identified caregiver or informant who is willing and able to provide follow-up information on the subject throughout the course of the study. This person must, in the opinion of the investigator, spend sufficient time with the subject on a regular basis such that the caregiver or informant can reliably fulfill the study requirements and must provide separate written consent. The caregiver or informant need not be living in the same residence as the subject. If the caregiver or informant is not residing with the subject, the investigator has to be satisfied that the subject can contact the caregiver or informant readily during the times when the caregiver or informant is not with the subject. If in doubt about whether a subject's care arrangements are suitable for inclusion, the investigator should discuss this with the medical monitor. At visits where the CDR or FAQ are conducted, caregivers or informants need to either attend the visit in person along with the subject or be able to be contacted by telephone at the time of the visit. The investigator will determine whether attendance in person is required or whether telephone contact will be suitable and will base this determination upon the functional ability of the subject among other factors.
 5. If receiving acetylcholinesterase inhibitors (AChEIs) or memantine, must have been on a stable dose for at least 12 weeks before the Baseline cognitive assessments at Visit 2, with no plans for dose adjustment in the foreseeable future. Treatment-naïve subjects can be entered into the study but there should be no plans to initiate treatment with AChEIs or memantine at the time of entry into the study.
 6. Must have been on stable doses of all other permitted chronically used concomitant medications (ie, not related to their cognitive decline) for at least 4 weeks before randomization

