- Systemic or ocular immunosuppressive or immunomodulatory drugs are not permitted for a period of 5 half-lives or 60 days (whichever is longer) before randomization. However, during the treatment period of the study, short term (not more than 14 days) use of steroids up to the equivalent of prednisolone 40 mg once daily is permitted after discussion with the Medical Monitor. Dosing with study drug should be suspended from the time steroid treatment is started. Complete blood count and lymphocyte subsets should be determined prior to starting steroid treatment and continue to be monitored weekly. Study drug may be resumed after discussion with the Medical Monitor when the following conditions are met: (1) treatment with steroids has been completed for at least 1 week; (2) absolute lymphocytes not <LLN; (revised per Amendments 07) (3) no lymphocyte subsets are below the discontinuation threshold (for Core Study only); (4) the investigator considers that the medical condition which required treatment with steroids has improved or resolved. Weekly testing of lymphocyte subset counts (for Core Study only) and CBC with differentials is required for 4 weeks following resumption of study drug administration. (revised per Amendment 04)
- (revised per Amendment 06)

Subjects who initiate treatment with an AChEI or memantine during the study, or who change their dose of AChEI or memantine while on study, will be allowed to continue in the study, but their clinical efficacy data will be censored from the time of drug initiation for any efficacy analyses. (revised per Amendment 05)

Subjects taking all other non-prohibited concomitant medications must meet the following requirements:

- Must be on stable dose for at least 4 weeks before randomization, except for medications that are administered as short courses of treatment or which are to be used intermittently as needed. Subjects who are on anticoagulants may have a variable dose but should have stable anticoagulation control for at least 4 weeks before randomization. They may be required to stop their anticoagulant medication prior to CSF collection and then restart this medication after the LP procedure, as per local guidelines. (revised per Amendment 04)
- Medications that are used as needed, rather than on a stable daily basis, and which are central nervous system (CNS) active and may affect cognitive function, are not permitted during a period of 72 hours before cognitive testing

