9.7.1.6.3 EXPLORATORY EFFICACY ANALYSES

(revised per Amendments 01, 02, 04, and 05)

An MMRM will be used to analyze the following exploratory endpoints:

- Change from baseline in CSF A β (1-40) and BACE1 variables (eg, activity and protein levels) from 4 weeks and up to 18 months. Data from early discontinuations will also be included. (revised per Amendment 04)
- Change from baseline in CSF biomarkers of neurodegeneration (eg, t-tau and p-tau) at 18 months of treatment
- Change from baseline in plasma amyloid measurements from 4 weeks and up to 18 months of treatment, and during posttreatment follow-up
- Change from baseline in CSF amyloid and CSF BACE1 measurements from 4 weeks and up to 18 months of treatment (revised per Amendment 06)
- Change from baseline in total hippocampal atrophy at 12 and 18 months as measured by vMRI
- Change from baseline in left and right hippocampal, whole brain, and total ventricular volume at 6, 12 and 18 months as measured by vMRI

- Change from baseline in Amyloid PET SUVR composite at 18 months for brain amyloid levels

The following efficacy endpoints will be summarized using descriptive statistics:

- Change from baseline in the clinical assessments: ADAS-cog₁₄, CDR, MMSE, ISLT, CBB, and FAQ at 12 weeks and at 6, 9, 12, 15, 18, 19, and 21 months

The relationship between efficacy endpoints and biomarker endpoints will be explored using correlation analysis.

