9.7.1.8.6 OTHER SAFETY ANALYSES

Cognitive decline will be assessed as a safety assessment, in addition to efficacy assessments. Cognitive assessments will include CBB ([Section 9.7.1.6](#)). (revised per Amendment 05)

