Listing 5 Strong CYP3A4 Inhibitors Prohibited Within 5 Half-Lives or 14 Days (Whichever Is Longer) Before Randomization Until After the Last Treatment Visit

| Generic name | Brand name(s) |
|----------------|--|
| boceprevir | Victrelis |
| clarithromycin | Clarithromycin, clarithromycin extended release, Prevpac |
| cobicistat | Tybost, Stribild, |
| conivaptan | Vaprisol |
| danoprevir | |
| elvitegravir | Vitekta, Stribild |
| indinavir | Crixivan |
| itraconazole | Sporanoz, Onmel |
| ketoconazole | Xolegel, Nizoral, Ketodan |
| lopinavir | Kaletra |
| nefazodone | Serzone |
| nelfinavir | Viracept |
| posaconazole | Noxafil |
| ritonavir | Norvir, Kaletra |
| saquinavir | Invirase, Fortovase |
| telaprevir | Incivek |
| telithromycin | Ketek |
| tipranavir | Aptivus |
| troleandomycin | Triocetin |
| voriconazole | Vfend, Voriconazole |

Note: This list is not exhaustive

Permitted Prior/Concomitant Medications

Listing 6 Medications Which Need To Be on a Stable Dose for 12 Weeks Before the Baseline Cognitive Assessments at Visit 2 and Remain on the Same Stable Dose from Baseline to Final Follow-Up Visit

| Generic name | Brand name (Names shown are not exhaustive and are examples only; names may be the [®] or [™]) |
|----------------------------|---|
| Cognitive Enhancers | |
| Donepezil | Aricept |
| Galantamine | Reminyl |
| Memantine | Namenda |
| Rivastigmine | Exelon |

Note: This list is not exhaustive.

Listing 7 Permitted Medications Used on PRN Basis Which are Not to be Used Within 72 Hours before Cognitive Testing

| Generic name | Brand name (Names shown are not exhaustive and are examples only; names may be the ® or ™) |
|---|---|
| Opiates | |
| Morphine | Astramorph PF, Avinza, Depo Dur, Duramorph, Infumorph, Kadian, MS Contin, MSIR, Oramorph SR, RMS, Roxanol |
| Opiate Agonists | |
| Codeine | Codeine |
| Fentanyl | Actiq, Duragesic, Fentora, Onsolis, Sublimaze |
| Meperidine | Demerol, Meperitab |
| Oxycodone | Dazidox, Endocodone, Eth-OxyDose, OxyContin, OxyFast, OxyIR, Percolone, Roxicodone, Roxicodone Intensol |
| Other opioids or opioid agonists which are used on PRN basis | |
| Benzodiazepines and sedatives | |
| Alprazolam | Alprazolam Intensol, Niravam, Xanax |
| Amitriptyline | (various) |
| Chlordiazepoxide | H-Tran, Librium |
| Clonazepam | Ceberclon, Klonopin |
| Diazepam | Diastat, Dizac, Valium |
| Dothiepin | (various) |
| Estazolam | ProSom |
| Flunitrazepam | Rohypnol |
| Flurazepam | Dalmane |
| Lorazepam | Ativan |

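### Section 9.4.7 starts AChEI/memantine censoring at drug initiation even for dose changers, whose initiation precedes baseline, so the rule as written discards all their clinical efficacy data

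*Protocol*

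**What the plan says.** Section 9.4.7 of the protocol names two triggers: "Subjects who initiate treatment with an AChEI or memantine during the study, or who change their dose of AChEI or memantine while on study". These subjects stay in the study, but their "clinical efficacy data will be censored from the time of drug initiation for any efficacy analyses". No other section gives a dose-change date as the start of censoring. The Amendment 06 text in the same file carries the same sentence, in its synopsis and in its Section 9.4.7.

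Inclusion criterion 5 (Section 9.3.1) says that a subject receiving these drugs "must have been on a stable dose for at least 12 weeks before the Baseline cognitive assessments at Visit 2". For untreated subjects, "there should be no plans to initiate treatment with AChEIs or memantine at the time of entry into the study". Appendix 2, Listing 6, classes the drugs as cognitive enhancers and expects subjects to "Remain on the Same Stable Dose from Baseline to Final Follow-Up Visit".

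On analysis, Section 9.7.1.6.3 introduces the Core clinical scales (ADAS-cog14, CDR, MMSE, ISLT, CBB, FAQ) with "The following efficacy endpoints will be summarized using descriptive statistics". Appendix 6 makes MMSE and FAQ secondary endpoints of the OLE Phase, as changes from both the Core and the OLE baselines. Cognition also has a separate safety role. Section 9.2.5 says "Cognitive decline will be assessed as a safety assessment during the Core Study", and Section 9.7.1.8.6 says "Cognitive decline will be assessed as a safety assessment, in addition to efficacy assessments".

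**The concern.** The sentence has two triggers and one start point, and the start point belongs to only one trigger. For a subject who begins an AChEI or memantine after randomization, initiation is the on-study event, and censoring from that date keeps everything before it. For a subject on the drug at entry whose dose changes later, initiation happened before baseline. Following the sentence removes that subject's clinical efficacy data altogether, including visits completed on a stable dose before the change.

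This matters for the statistical analysis plan. A plan that follows the protocol discards valid data, and a plan that uses the sensible date departs from the protocol. The same open wording carries into the OLE Phase, where an event in Core would still censor a subject who has been stable since before the OLE baseline.

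A second issue is selection. The drugs are cognitive enhancers and starts are not planned at entry, so an on-study start or change could be a response to the decline being summarised. If so, descriptive means of the remaining subjects understate decline.

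**Working it through.** **1. Date of initiation against date of the trigger**

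| Subject | Trigger | Initiation | Data kept under the literal rule |
|---|---|---|---|
| Not treated at entry | on-study start | date of the start | all visits before the start |
| On the drug at entry | on-study dose change | at least 12 weeks before the Visit 2 cognitive tests (criterion 5) | none |

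**2. Core visits lost by a dose changer**

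Section 9.7.1.6.3 lists clinical assessments at 12 weeks and at 6, 9, 12, 15, 18, 19 and 21 months. On the Table 7 schedule these are weeks 12, 26, 39, 52, 65, 78, 82 and 90, which is 8 post-baseline visits. A visit on the day of the change is counted as kept.

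| Dose change at week | Kept, literal rule | Kept, counted from the change |
|---|---|---|
| 26 | 0 of 8 | 2 of 8 |
| 39 | 0 of 8 | 3 of 8 |
| 52 | 0 of 8 | 4 of 8 |
| 65 | 0 of 8 | 5 of 8 |

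The baseline value is lost too under the literal rule.

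**3. Reach into the OLE Phase**

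Section 9.4.7 introduces its medication listings for both the Core Study and the OLE Phase. The OLE schedule (Table 14, note l) refers back to Section 9.4.7, and Appendix 6 states no censoring rule of its own. Table 14 schedules MMSE and FAQ after Visit 21 at Visits 25 to 32 and at Visits 33 and 34: 8 + 2 = 10 visits. A subject who starts or changes the drug in Core is already past the censoring date at Visit 21. Read literally, 0 of 10 enter the efficacy summaries, including change from the OLE baseline.

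**4. Possible understatement of decline (assumption only)**

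The plan has no figure of its own here. Its only relevant number is the arm size of 15, and 60/4 = 15 agrees with it. The documents do not give the share of subjects who start or change the drug, or how that relates to decline.

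Assume standardised 18-month decline is normal, the liability to start or change has correlation ρ with it, and the fraction p with the highest liability is censored. The mean decline of those left is then too small by

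ρ × φ(z₁₋ₚ)/(1 − p) SD.

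The factor φ(z₁₋ₚ)/(1 − p) is 0.195 for p = 10%, 0.350 for 20% and 0.497 for 30%.

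| ρ | p = 10% | p = 20% | p = 30% |
|---|---|---|---|
| 0 | 0 | 0 | 0 |
| 0.3 | 0.06 | 0.10 | 0.15 |
| 0.5 | 0.10 | 0.17 | 0.25 |
| 0.8 | 0.16 | 0.28 | 0.40 |

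A simulation of 400,000 subjects per cell gave 0.095, 0.175 and 0.247 at ρ = 0.5, in agreement. An arm of 15 keeps on average 15 × 0.9 = 13.5, 15 × 0.8 = 12 or 15 × 0.7 = 10.5 subjects. These figures apply to a late visit by which all the events have occurred. They are smaller at earlier visits, because starters keep their earlier data.

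**The case against.** The best reply is that nobody would apply the sentence literally. It speaks of initiation during the study, so the intended start is presumably the on-study event, and deleting a baseline because of a month-12 dose change makes no sense as a purpose. That is a fair guess at intent. It does not repair the rule: the dose-change trigger is explicit, its date is not, and no other section supplies it.

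On the OLE Phase, the sentence is tagged to Amendment 05 and the OLE came with Amendment 07, and Table 14 refers to Section 9.4.7 for medications rather than analysis. The OLE reach is therefore a consequence of the literal text and may not be intended. It still needs a sentence to settle it.

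Three stronger readings are tempting, and the documents do not support them.

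- A reader might infer that the rule hides cognitive harm from the safety review. It is confined to efficacy analyses. Cognition is summarised separately as safety in Core (Section 9.7.1.8, with CBB as the example) and in the OLE (MMSE, Appendix 6), and the cross-reference from Section 9.7.1.8.6 to 9.7.1.6 imports no censoring. Section 9.5.1.5.1 also has decline judged excessive reported as an adverse event.
- A reader might infer that the rule removes the fastest decliners. That is plausible but not shown. A dose change can be a reduction for tolerability, Listing 6 expects stable doses, and no rates are given.
- A reader might infer that censoring is the wrong primary handling. Censoring keeps the effect of a symptomatic drug out of the scales, and data after the change could themselves understate decline. Which summary leads is an estimand choice.

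**Conclusion.** The concern holds as an error in a stated analysis rule. For a subject on an AChEI or memantine at entry who changes dose, Section 9.4.7 as written discards all clinical efficacy data: 8 of 8 post-baseline Core visits, against 4 of 8 kept if counted from a week-52 change. This follows from Section 9.4.7 and inclusion criterion 5 and needs no assumption. Read literally, a Core start or change also removes the subject from every OLE efficacy summary of MMSE and FAQ.

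Understatement of decline is possible, and its size is assumed: about 0.10 to 0.25 SD if 10% to 30% are censored at a correlation of 0.5, and zero if censoring and decline are unrelated. New starters lose only data after the start.

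The impact is limited. The scales are exploratory and descriptive in Core and secondary in the OLE, there is no primary efficacy endpoint, and the safety summaries of cognition are outside the rule.

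**What to change.** In Section 9.4.7, and wherever the synopsis repeats the sentence:

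1. Replace the start point with: *from the date of on-study initiation or first on-study dose change, whichever triggers the rule*.
2. State that, for change from the OLE baseline, the rule applies only to starts or dose changes after Visit 21.
3. Add a supplementary descriptive summary of all observed clinical data regardless of AChEI or memantine change, with the number of censored subjects by arm.

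The third item leaves the choice of leading summary open and lets a reader see whether censoring matters. The cost is the wording change and one extra set of descriptive tables. No new data are needed, because these subjects are allowed to continue in the study.

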9.4.8 Treatment Compliance

Records of treatment compliance for each subject will be kept during the Treatment Period. CRAs will review treatment compliance during site visits and at the completion of the study.

9.4.9 Drug Supplies and Accountability

In compliance with local regulatory requirements, drug supplies will not be sent to the investigator (or if regionally required, the head of the medical institution or the designated pharmacist) until the following documentation has been received by the sponsor:

- A signed and dated confidentiality agreement
- A copy of the final protocol signature page, signed and dated by both the sponsor and investigator
- Written proof of approval of the protocol, the ICFs, and any other information provided to the subjects by the IRB/IEC for the institution where the study is to be conducted
- A copy of the IRB/IEC-approved ICF and any other documentation provided to the subjects to be used in this study
- The IRB/IEC membership list and statutes or Health and Human Services Assurance number
- A copy of the certification and a table of the normal laboratory ranges for the reference laboratory conducting the clinical laboratory tests required by this protocol
- An investigator-signed and dated FDA Form FDA 1572, where applicable
- Financial Disclosure form(s) for the principal investigator and all subinvestigators listed on Form FDA 1572, where applicable
- A signed and dated curriculum vitae of the principal investigator including a copy of the principal investigator's current medical license (required for United States sites) or medical registration number on the curriculum vitae
- A signed and dated Clinical Trial Agreement (CTA)
- A copy of the regulatory authority approval for the country in which the study is being conducted (if required), and the Import License (if required)

The investigator and the study staff (or if regionally required, the head of the medical institution or the designated pharmacist) will be responsible for the accountability of all study drugs (dispensing, inventory, and record keeping) following the sponsor's instructions and adherence to GCP guidelines as well as local or regional requirements.

Under no circumstances will the investigator allow the study drugs to be used other than as directed by this protocol. Study drugs will not be dispensed to any individual who is not enrolled in the study.

The site must maintain an accurate and timely record of the following: receipt of all study drugs, dispensing of study drugs to the subject, collection and reconciliation of unused study drugs that are either returned by the subjects or shipped to site but not dispensed to subjects, and return of reconciled study drugs to the sponsor or (where applicable) destruction of reconciled study drugs at the site. This includes, but may not be limited to: (a) documentation of receipt of study drugs, (b) study drugs dispensing/return reconciliation log, (c) study drugs accountability log, (d) all shipping service receipts, and (e) documentation of returns to the sponsor. All forms will be provided by the sponsor. Any comparable forms that the site wishes to use must be approved by the sponsor.

The study drugs and inventory records must be made available, upon request, for inspection by a designated representative of the sponsor or a representative of a health authority (eg, FDA, Medicines and Healthcare Regulatory Agency). As applicable, all unused study drugs and empty and partially empty containers from used study drugs are to be returned to the investigator (or if regionally required, the head of the medical institution or the designated pharmacist) by the subject and, together with unused study drugs that were shipped to the site but not dispensed to subjects, are to be returned to the sponsor's designated central or local depot(s) during the study or at the conclusion of the study, unless provision is made by the sponsor for destruction of study drugs and containers at the site. Destruction at the site will only occur under circumstances where regulation or supply type prohibits the return of study drugs to the central or local depot(s). Approval for destruction to occur at the site must be provided by the sponsor in advance. Upon completion of drug accountability and reconciliation procedures by the site's personnel and documentation procedures by the sponsor's personnel, study drugs that are to be returned to the sponsor's designated central or local depot(s) must be boxed, sealed, and shipped back to the central or local depot(s) following all local regulatory requirements. In some regions, study drugs may be removed from the site and hand delivered to the central or local depot by sponsor representatives. Where study drugs are approved for destruction at the site, destruction will occur following the site's standard procedures and certificates of destruction will be provided to the sponsor.

Drug accountability will be reviewed during site visits and at the completion of the study.

